### 1.0 Objective

New approaches to treating substance use disorders (SUDs) are desperately needed. We aim to develop novel neurostimulation using temporal interference technology to treat SUDs, with the long-term goal of developing a lightweight, inexpensive headband that can suppress the wearer's cravings and support drug abstinence indefinitely. To do this, we will explore newly developed non-invasive deep brain electrical stimulation methods that allow penetration to deep brain structures, especially those that are central to reinforcement of addiction, without stimulating the overlying cortex. We will test our methods first in subjects with nicotine use

disorders. We propose to compare feasibility and tolerability of temporal interference stimulation against existing transcranial direct current stimulation, which has been studied in SUDs, but has limited efficacy given its inability to stimulate deep brain regions.

**Specific Aim:** To investigate whether stimulation with a mild current from temporal interference non-invasive deep brain stimulation (TI-NDBS) to the Anterior Cingulate Cortex (ACC), the anterior insula (AI), or the nucleus accumbens (NAcc) will reduce nicotine craving and seeking. The TI-NDBS is similar to the traditional transcranial direct current stimulation (tDCS), a method approved for use in a number of other studies in our department. Other studies have shown there have been some effects of reducing craving with tDCS (Fregni, Liguori, et al., 2008), however, tDCS cannot stimulate structures such as the ACC very effectively because tDCS cannot stimulate deeper brain regions. Thus, the Specific Aim ultimately will compare TI-NDBS with tDCS and sham stimulation. The first phases (Phases 1 and 2) of this aim investigate the effects of TI-NDBS on sensations, craving, and brain activity. The second set of phases examine the effects of TI-NDBS on nicotine seeking using a Nicotine Delivery Device (NDD) and craving in comparison with sham (Phase 3) and tDCS and sham (Phase 4).

## 2.0 Background

This project aims to develop a line of research using new non-invasive neurostimulation technology to treat adults with substance use disorders (SUDs). SUDs are a severe, current problem in Indiana and across the US, with many lives lost daily to overdoses and other medical complications. In the short term, we aim to identify novel target brain regions for neurostimulation treatment and characterize their effects behaviorally and neurally. A number of case reports in humans describe complete, permanent, and near effortless disruption of SUDs due to direct effects on specific brain regions and circuits known to be involved in the addiction process, such as the insula, the nucleus accumbens (NAcc), the dorsolateral prefrontal cortex (DLPFC), and the amygdala (Naqvi & Bechara, 2014). For instance, Naqvi et al. (2007, *Science*) described cases in which smokers spontaneously lost all interest in cigarettes following stroke damage to the bilateral anterior insula (AI). Similarly, Müller et al. (2009, *Pharmacopsychiatry*) describes cases of permanent remission of alcoholism due to deep brain stimulation of the NAcc after years of 2+ liter/day hard liquor consumption. The AI assists with predictions of future affective bodily states, such as satiety, pain, craving, etc. (Craig, 2002).

Given these findings, it is likely that the AI represents internal affective states related to drug use, such as craving, drug reward, withdrawal, adverse health effects, successful self-control and abstinence, and the anticipation of each of these states. Likewise, error-related activation of the nearby amygdala is greater in subjects who are more likely to fail treatment for addiction (Forster et al., 2017).

When considering cases of significant damage caused by clinical pathology (e.g., lesion from stroke), deep brain areas have shown to exhibit a variety of outcomes. In the anterior cingulate (ACC), the most consistent and substantial report has been an expression of akinetic mutism; those with ACC lesions are un-willing/motivated to produce voluntary motor responses (Devinsky et al., 1995). Damage to AI regions through stroke lesions have presented with widely varying effects, including a slower capacity in switching between different cognitive tasks (set-

switching; Varjacic et al., 2018), or a higher pain sensitivity to noxious stimuli (e.g., cold tolerability; Starr et al., 2009). Therefore, the lesions to AI exhibit a large variety in changes to cognitive and behavioral states. In terms of the NAcc, the understanding regarding the effects of impact to humans is based almost exclusively on trials using deep brain stimulation of the NAcc in clinical populations, such as obsessive compulsive disorder (Huff et al., 2010), alcohol dependency treatment (Kuhn et al., 2007), and addiction to smoking (Kuhn et al. 2007). The effects of altering NAcc through stimulation have shown a variety of results, including cessation of smoking or alcohol dependency (Kuhn et al., 2007), or increased risky decision making during cognitive tasks (Nachev et al., 2015). Therefore, alteration of NAcc function through DBS has shown a variety of outcomes. These types of findings, as well as those previously discussed, have led to a possible link to underlying addiction states. Importantly, these examples are extreme clinical cases in which substantial affliction to these brain areas or deep brain implantation (which uses larger levels of voltage exceeding 3 V/mm). Thus, methods that offer a safe and non-invasive, reversible modulation of neural activity in the AI, NAcc, and ACC in particular are likely to be effective at treating addiction without inducing any of the effects subsumed by lesions.

On Oct. 12, 2018 we received funding from the IU Grand Challenge Addictions program to examine the effects of neurostimulation on nicotine/drug craving and seeking, which is the focus of this protocol. We will be stimulating specific brain areas that we have found to be centrally involved in nicotine seeking (with our approved companion protocol on gambling for nicotine inhalations) using the nicotine delivery device (NDD) that we use in the MRI scanner with smokers. Our companion protocol studies found so far that activation in the dorsal ACC (anterior cingulate cortex) occurred just prior and right after the subject gambled to obtain a nicotine dose; once satiated on nicotine, the ACC was no longer activated and the subject did not seek more nicotine. In addition to the ACC, the ventral striatum also was activated while seeking nicotine. The overarching purpose of this project is to test the feasibility and effectiveness of stimulating these brain areas using temporal interference non-invasive deep brain stimulation method (referred to here as TI-NDBS) with the idea that such stimulation may be ultimately used as a treatment component for nicotine addiction, and eventually for opiate addiction, since these brain areas are centrally involved in addiction in general. TI-NDBS is similar to other commonly used low voltage/current brain stimulation approaches, such as transcranial direct current stimulation (tDCS) and transcranial alternating current stimulation (tACS), which, to date, have only shown the side-effect of mild skin irritation in tDCS but not tACS (reviewed in Matsumoto and Ugawa, 2017). Thus, non-invasive electrical neurostimulation methods including TI-NDBS all induce such a low level of voltage in the brain (0.8 V/m) that these methods can only modulate ongoing neural activity in a weak manner. Because TI-NDBS is identical in delivery type and amount of energy to tACS and no previous studies have reported a side effect with tACS, this indicates there is little to no risk for adverse reactions to TI-NDBS. Essentially, to date, there is no reported negative side-effects for any non-invasive electrical neurostimulation method, demonstrating their safety (Matsumoto and Ugawa, 2017). The IRB has already approved tDCS/tACS for ongoing studies in other labs at IU, for example the Hetrick lab. The difference between TI-NDBS and tDCS/tACS is that stimulation can be localized better with TI-NDBS; *notably, TI-NDBS being more localized does not mean it is stronger, the stimulation is just more confined to the intended brain region.* TI-NDBS stimulation consists of multiple electrode pairs administering tACS, except

it is far superior as the localization of stimulation to deep brain sites is much better.

Because TI-NDBS is essentially identical to tACS (and almost identical to) tDCS stimulation, which both have been applied to deep brain regions previously and found no side effects. This indicates there is no historical evidence for any expected negative consequence of using TI-NDBS on the same brain regions. For example, tACS directed towards ACC (Onoda et al., 2017) found weak, non-persistent changes in reports to emotionally valanced stimuli. Other studies of tACS on the ACC have found no adverse effects (Chander et al. 2016), nor have studies that broadly target the prefrontal cortex and would likely affect the nucleus accumbens and insula (Vanneste et al. 2013). Along these lines, tDCS directed at AI (Li et al., 2018) only had a reported effect of increasing participant alertness and mild and transient changes in brain network activity assessed using fMRI. With respect to TI-NDBS, previous testing has been completed with animals at currents equivalent to that normally applied in human studies (~ 2 mA), and the histological assays looking for tissue damage found no evidence of harm (Grossman et al., 2017). Together, the commonality between TI-NDBS and existing methods, and the complete absence of any reports of damage or harm from more common methods (tACS/tDCS), this indicates that TI-NDBS should be equally safe and tolerable for neurostimulation.

Given that other studies have shown effects of reducing craving with tDCS (Fregni, Liguori, et al., 2008) when stimulating deep brain areas, while tDCS lacks the focal control afforded to TI-NDBS, our proposal aims to employ TI-NDBS as a more accurate means to stimulate different brain targets previously linked to addiction. There are 4 phases to the protocol. Phase 1. A pilot study of acceptance of TI-NDBS (assessing the subjects subjective mood and sensations during stimulation), Phase 2. A pilot localization study where TI-NDBS will be done in the MRI scanner and the exact location of stimulation will be established with specific scalp electrode placements. Phase 3 will examine the effects of TI- NDBS and sham on nicotine craving and inhalations using our nicotine inhalation device already approved in another of our IRB protocols and Phase 4 will compare the effect of TI-NDBS, with traditional tDCS, and sham on nicotine craving and inhalations.

electrode placement. The software simulates the electrical fields generated given a set of electrode locations in the 10/20 coordinate system. With this, we are able to specify a target brain region, then run a software optimization routine that determines the optimal electrode placement to target the desired brain region. After some *in silico* testing, we found that the electrode placement can be determined in the standard 10/20 coordinate system using a standard brain image template (the Montreal Neurological Institute or MNI template.) Furthermore, once the electrode locations are calculated, they can be applied to all subjects without subject-specific structural MR images, because the between-subject variation in 10/20 coordinates vs brain regions is small relative to the extent of the temporal interference region. Put another way, the marginal increased accuracy due to optimization on a subject-specific structural MR image vs. an MNI template brain is negligible. This will allow us to determine the electrode placements with high accuracy, so that we can specifically target the desired brain regions.

**Phase 1. Tolerability.** In phase I, we will test the safety of the temporal interference non-invasive deep brain stimulation (TI-NDBS) device on non-smokers (n=3). Subjects will be administered a questionnaire to assess their physical experiences and sensations using a 5-point Likert-scale (Stimulation experience scale attached in Notes & Attachments and is the same scale used in all four stages of the protocol). After baseline measures, subjects will be sitting in a chair and have the electrodes (measuring approximately 2 cm by 2 cm) attached to the scalp.

TI-NDBS will be a very small electric current applied to the brain through the scalp electrodes. The subjects will receive stimulation for 30 minutes. Electrodes will be placed around the head in positions designed to maximize focal stimulation of the anterior cingulate cortex, anterior insula, or nucleus accumbens. The skin beneath the electrodes will be cleaned prior to application, and a saline solution or gel will be used to help to attach the electrode to the scalp. There will be a small current of electricity (2 mA peak-to-peak alternating current per electrode pair) that will run through the electrodes. There will be a maximum of 2 mA per electrode pair and no single region will receive more than 2 mA, although there will be two pairs of electrodes, which each apply up to 2mA at separate sites. At the beginning of every period of stimulation, the current will increase slowly at a constant rate for 30 seconds until it reaches the appropriate intensity. At the end of the stimulation, the current will decrease slowly for 30 seconds until it reaches zero. Some tingling under the electrodes may be felt, and subjects may also see flashing lights. Subjects will also be able to stop the experiment at any time if the subject wants to stop or indicates significant discomfort. Right after half the stimulation period has elapsed, the subject will complete the stimulation experience scale again at the end of the stimulation period (condition assignment based). Then the subject will go to the restroom to clean off any gel that remains on the skin. The gel washes away easily with water. Ten minutes after the end of the stimulation, the subject will complete the stimulation experience scale again reporting on their feelings and sensations at that moment. The entire testing process will last about 1.5 hour. Phase 1 will be completed before we begin Phase 2. Testing will take place at IU Bloomington, Department of Psychological and Brain Sciences.

#### Safety and Monitoring:

- (1) **Comfort:** Subjects will be asked to rate (1-5 scale) severity, location and quality (self described) of any discomfort immediately prior to the stimulation, at 5 and 15 minutes during stimulation, immediately after the stimulation and at 10 minutes after the stimulation. If any discomfort persists at 10 minutes after stimulation, treatment and ongoing assessment will be arranged as needed by the study physician.
- (2) **Cognitive Effects:** Baseline memory, attention and verbal reasoning will be assessed using the Digits span test from the WAIS, which assesses short-term memory and attention. This will be repeated 10 minutes after the stimulation. Subjects will also be asked open ended

questions about any changes in their thinking or cognitive status. Research staff will contact subjects between days 2 and 5 after scanning to query the persistence or emergence of any cognitive changes.

(3) **Psychiatric Effects:** Emotional, motivational and behavioral symptoms will be assessed before stimulation and immediately following stimulation. Subjects will be contacted to follow up between days 2 and 5 after scanning to query the persistence or emergence of any changes to their emotions, motivation or behavior. This testing will involve using the PANAS-SF test of positive and negative affect.

**In the unlikely event of serious adverse events occurring in Phase 1, the study team will report back to the DSMB and the IRB to assess whether or not the study could proceed to Phases 2-4.**

**Phase 2. Neural effects.** In Phase II, subjects will complete the MRI safety screen questionnaire and the stimulation experience scale (the same scale from phase 1) prior to entering the MR scanner. The electrodes (2 cm x 2 cm) will be attached and subjects will enter the MR scanner and the TI-NDBS stimulation will be administered while in the scanner, alternating 2-minute stimulation and 2-minute no-stimulation periods. Subjects may alternatively receive stimulation from all electrodes at the same frequency in order to make comparisons to temporal interference stimulation. For every two minute period of stimulation, the current will increase slowly at a constant rate for 30 seconds until it reaches the appropriate intensity. At the end of the stimulation, the current will decrease slowly for 30 seconds until it reaches zero. For sham stimulation, the current will increase during a 30 second interval and then immediately decrease back to zero over a 30 second interval, for a total of 60 seconds of stimulation. This will allow us to identify immediate neural activation due to stimulation, while controlling for any scalp sensations with the sham condition. The electrodes will be placed to target stimulation at either anterior Cingulate or nucleus accumbens. Immediately following the stimulation session, subjects will complete the stimulation experience scale and then will clean off residual electrode gel. The stimulation experience scale is administered again 30 minutes later. The subject will be in the scanner for about 1 hour.

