conventional transcranial direct current stimulation for smoking reduction. To test this, we will recruit another group of subjects who are heavy smokers into three groups, then ask them to abstain from smoking. Prior to stimulation, subjects will be given the NDSS to determine baseline nicotine dependence. The first group will receive standard transcranial direct current anodal stimulation of the right DLPFC and cathodal stimulation of the left DLPFC (F3 and F4 in the 10/20 system). The second group will receive TI-NDBS to either the nucleus accumbens or anterior insula or anterior cingulate, depending on which is found to be more effective in Phase 3. The third condition will be sham. The strength of the stimulation and duration will be the same as in previous phases. Prior to stimulation, subjects will be administered a questionnaire to assess their physical experiences and sensations using a 5-point Likert-Scale. Immediately after stimulation, subjects will complete the stimulation experience scale, then complete the scale again 30 minutes later. In addition, we will assess craving levels every 10 minutes during the stimulation period. We will repeat this for five consecutive days. We will then follow up with subjects every day, up to three times per day, for 1 week after starting the tDCS, using EMA via a free smartphone app (ilumivu.com) to monitor cigarette use and craving. The questions that will be used in the app are in a script attached (see EMA follow up questions). We will compare the sham vs. tDCS vs. TI-NDBS groups to identify differences in craving and relapse. We expect to find that TI-NDBS leads to reduced craving and drug use relative to sham or tDCS. The procedure in this phase will not add anything new, except testing subjects with tDCS in addition to TI-NDBS and sham.

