## **6.0 Statistical Analysis and Sample Size:**

In phase 1, we will assess tolerability with an initial cohort of 3 stimulation subjects. Our aim here is to identify any potential adverse effects, using two approaches. We will monitor the stimulation condition for clinically significant adverse effects such as seizures, prohibitive pain, etc, though we do not expect this based on all the literature from earlier studies.

In phase 2, we will conduct a pilot assessment to determine whether and how the stimulation immediately influences neural activity. As this is a within-subjects pilot design intended to estimate the effect size of neural activation, we will scan 10 subjects, comparing the neural activation in each subject during the stimulation period with neural activation in the same subject during the no-stimulation periods. We do not have a power analysis for this phase yet, because the whole point is to perform a pilot study in order to estimate the effect sizes. We anticipate that 10 subjects will be sufficient to estimate the effect sizes.

In phase 3, we will proceed in two parts. During the first pilot part, we will recruit 5 subjects in each of 3 groups, to identify which two of the three candidate brain regions seem most promising sites of stimulation to reduce nicotine craving and consumption. Once we identify the two more promising sites of stimulation, we will proceed to the second part. We do not have a power analysis for this part because again, we are looking to estimate the relative effect sizes for one stimulation site compared to another. For the second part, we will recruit 45 subjects who are heavy smokers into three groups of 15 each, then ask them to abstain from smoking for several hours prior to the session. The first group will receive TI-NDBS over the most promising site. The second group will receive TI-NDBS over the second most promising site. The third group will receive sham stimulation. We will measure total real-time ad lib nicotine vapor inhalation during a 60 minute stimulation session, and every ten minutes, we will ask subjects to

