In phase 4, we will compare TI-NDBS vs. conventional transcranial direct current stimulation for smoking reduction. To test this, we will recruit another 45 subjects who are heavy smokers into three groups of 15 each, then ask them to abstain from smoking. The first group will receive standard transcranial direct current anodal stimulation of the right DLPFC and cathodal stimulation of the left DLPFC (F3 and F4 in the 10/20 system). The second group will receive TI-NDBS to the most promising site as determined in phase 3. The third condition will be sham. We will assess craving levels every 10 minutes during the 60 minute stimulation period. We will repeat this for five consecutive days. We will then follow up with subjects 1 week after starting the tDCS, using ecological momentary assessment (EMA) via smartphone apps (ilumivu.com) to monitor cigarette use and craving. We will compare the sham vs. tDCS vs. TI-NDBS groups to identify differences in craving and relapse. **Analysis and predictions:** We expect to find that TI-NDBS leads to reduced craving and drug use relative to sham or tDCS. We will carry out the same statistical tests as in Study 1. As before, we do not yet know the effect sizes but will aim to estimate them based on the initial 45 subjects.

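### Phases 3 and 4 list no delayed cognitive or mood query after the longest and the repeated stimulation, although Phase 1 has one at days 2 to 5

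*Combined protocol and SAP*

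**What the plan says.** Exposure, from 3.0 Design and 6.0 Statistical Analysis and Sample Size:

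- Phase 1, 3 non-smokers, one session: "The subjects will receive stimulation for 30 minutes".
- Phase 2, 10 subjects, about an hour in the scanner: "alternating 2-minute stimulation and 2-minute no-stimulation periods". The Phase 2 safety text refers to a second and a third session.
- Phase 3: "We will measure total real-time ad lib nicotine vapor inhalation during a 60 minute stimulation session".
- Phase 4, 60-minute sessions: "We will repeat this for five consecutive days".

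On Phase 4, 3.0 Design states "The strength of the stimulation and duration will be the same as in previous phases" and "The procedure in this phase will not add anything new, except testing subjects with tDCS in addition to TI-NDBS and sham". The TI device text in 3.0 gives the full session as 40 minutes.

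Delayed follow-up, from the Safety and Monitoring lists in 3.0: Phase 1 has a staff contact at days 2 to 5 about cognition and, separately, about emotion, motivation and behavior: "Subjects will be contacted to follow up between days 2 and 5 after scanning to query the persistence or emergence of any changes". Phase 2 has a cognitive query at the later sessions and 5 to 14 days after the third. The Phase 3 and Phase 4 lists have neither.

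Oversight: the Phase 1 list says "In the unlikely event of serious adverse events occurring in Phase 1, the study team will report back to the DSMB and the IRB", who then assess whether Phases 2 to 4 can go ahead. The TI device text sends adverse reactions to the IRB and DSMB and early terminations to the IRB. Section 7.0 Data Management adds day-to-day monitoring by the principal investigator, an annual formal evaluation, and the possibility of ending the study early for adverse events.

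**The concern.** The delayed query is present where exposure is lowest and absent where it is highest. The sponsor judged it worth asking, days after a single half-hour session, whether thinking or mood had changed. No reason is given for dropping the question once sessions last an hour or are repeated daily. The plan's own safety discussion cites a tDCS study with an effect still present at 6 months, so it does not treat after-effects as confined to the session.

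If a change appeared or lingered after the Phase 3 session, or after the full Phase 4 course, no listed assessment would ask about it. Finding it would depend on the subject volunteering it, or on EMA items that the documents do not show. The statement that Phase 4 adds nothing except tDCS makes this harder for an IRB or DSMB to notice, because the five-day repetition is also new.

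**Working it through.** The plan gives no figure to reproduce here. The check compares exposure and safety schedules, then works out timing and cost.

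**1. Exposure**

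- Phase 1: 1 × 30 = 30 minutes.
- Phase 2: about 60 minutes in the scanner, half of it on, so at most about 60 × 1/2 = 30 minutes per session. With three sessions (inferred from the safety text), at most 3 × 30 = 90 minutes.
- Phase 3: 1 × 60 = 60 minutes. Session ratio to Phase 1: 60/30 = 2.0. If the 40 minutes in the TI device text applied instead: 40/30 = 1.33.
- Phase 4: 5 × 60 = 300 minutes over five days.

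**2. Schedules side by side**

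| Phase | Last timed cognitive test | Last timed mood scale | Delayed query listed |
|---|---|---|---|
| 1 | Digit span, 10 min after | PANAS-SF, immediately after | Cognitive and psychiatric, days 2–5 |
| 2 | Digit span, 10 min after | PANAS, immediately after | Cognitive only, at later sessions and 5–14 days after the third |
| 3 | Digit span, 10 min after | PANAS, immediately after | None |
| 4 | Digit span, 10 min after | PANAS, immediately after | None |

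Phases 3 and 4 also repeat the stimulation experience scale at 30 minutes, but it covers physical experiences and sensations. Their open-ended cognitive questions have no stated time.

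**3. What Phase 4 already covers.** If the listed checks are done at every session, those before sessions 2 to 5 give next-day information on sessions 1 to 4. Nothing is listed after session 5, so the completed course is the part left out.

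**4. Where a day 2–5 query would fall.** In Phase 3, days 2 to 5 after the only session lie inside the one-week EMA. In Phase 4 the last session is on day 5, so the window is 5 + 2 = day 7 to 5 + 5 = day 10. EMA for one week from the start, as the Phase 4 text has it, ends at about day 7 and misses most of the window. EMA for two weeks after stimulation, as the New technology text has it, would run to 5 + 14 = day 19 and cover it.

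**5. Subjects affected.** Phase 3: 3 × 5 = 15 in the pilot part plus 3 × 15 = 45 in the second, 60 in all. Phase 4: 3 × 15 = 45. Total 60 + 45 = 105.

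**6. Context only.** With no events in n subjects, the one-sided 95% upper limit on the event rate is 1 − 0.05^(1/n): 63% for the 3 Phase 1 subjects, 18% for the 15 in the Phase 3 pilot part, and 6.4% for the 15 + 30 = 45 given TI-NDBS by the end of Phase 3. The chance that 3 subjects show at least one event is 1 − 0.95³ = 14% or 1 − 0.90³ = 27% for assumed true rates of 5% or 10%. A clean Phase 1 says little by itself, but these figures do not establish the follow-up gap.

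**The case against.** The strongest reply is that oversight does not stop at Phase 1. A reader might infer from the Phase 1 wording that exposure rises with no safety decision behind it. The documents do not support that. The Phase 1 rule is triggered by serious events; the TI device text has a lower trigger, any adverse reaction, with reports to the IRB and DSMB. Section 7.0 allows early ending, and discomfort persisting at 10 minutes goes to the study physician in every phase. What is absent is a scheduled pooled look before the second part of Phase 3 and before Phase 4. That is good practice at most, and it would need a decision rule to be useful.

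A reader might also infer a tenfold dose from 300/30 = 10. That adds minutes over separate days, and nothing in the documents says effects accumulate in that way. Current stays at no more than 2 mA per electrode pair.

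Third, the phase lists may be incomplete. The TI device text mentions heart rate, blood pressure and psychiatric symptoms among the assessments, and the first two are in neither the Phase 3 nor the Phase 4 list. Subjects are prompted up to three times a day, and the EMA script is an attachment not supplied. So it cannot be said that delayed changes would be missed, only that no described assessment asks about them. This limits the confidence of the point without removing it, because all three descriptions of EMA content in 3.0 name smoking or vaping and craving.

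Fourth, "The strength of the stimulation and duration will be the same as in previous phases" is right relative to Phase 3. It is wrong only relative to Phases 1 and 2.

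**Conclusion.** The point stands as an inexpensive safety improvement. The sponsor's own day 2–5 cognitive and psychiatric query is not listed after the 60-minute Phase 3 session or after the last of the five Phase 4 sessions, and 105 subjects are affected. Session length doubles from Phase 1, and daily repetition over five days is new in Phase 4, contrary to "The procedure in this phase will not add anything new, except testing subjects with tDCS in addition to TI-NDBS and sham". The 40-minute figure conflicts with the 60 minutes given for Phases 3 and 4.

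This rests on three assumptions: that the EMA script contains what the text describes; that the Phase 1 contact window, worded as counted from scanning, means from the stimulation session; and that 60 minutes is the intended session length. If the script already asks about thinking and mood, what remains is the length of the Phase 4 EMA and the wording corrections.

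**What to change.** 1. Add the Phase 1 cognitive and mood query to Phases 3 and 4, in all arms including sham, between days 2 and 5 after the last session. The design is single-blind and the experimenter knows the current, while craving and smoking are being self-reported in the same week. The query should therefore be fixed-script items in the EMA app, placed after the craving and smoking items, or be asked by staff unaware of arm. Reported changes should go to the study physician.
2. Run the Phase 4 EMA at least to day 10 from the first session. The two-week period in the New technology text already does this; the one-week wording should be brought into line.
3. Correct the Phase 4 text to say that five consecutive daily sessions are new and that the 60-minute session is longer than in Phase 1. Change 40 minutes to 60 in the TI device text.
4. Optional: a DSMB look at pooled safety data before the second part of Phase 3 and before Phase 4, where the plan already pauses to choose sites, with a stated rule for holding.

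The cost of items 1 to 3 is a few extra questions for 105 subjects, someone to read the answers, and about three more days of Phase 4 EMA (day 7 to day 10) if the one-week version is the one in use. Current, session length and sample size do not change.
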